6. STATISTICAL PLAN AND CONSIDERATIONS

Sample size estimation:

The sample size for this study is a total of 40 subjects (20 HBP and 20 CS lead). The sample size estimate was based on a goal to observe an absolute 10% difference in LVEF between the two groups, leading to a Cohen's d statistic of 1. With a significance level (α) = 0.05 and a power of 0.8, at least 17 subjects will be required in each group. A goal of 40 subjects was made to allow for possible dropout during the study period.

Statistical methods:

Patients will be studied based on the final treatment allocation. Crossovers and reasons for crossover will also be recorded. Fisher's exact or the Chi-Square test will be used for categorical variables, and continuous parameters will be compared by the two-tailed unpaired Student's t test and the F test for analysis of variance (ANOVA), as needed. Kaplan-Meier method will be used for computing the event free survival curves. Each implant strategy will be compared within this cohort of patients for its impact on percent change QRS duration, LVEF, and as clinical outcome. Multiple logistic regression and multiple regressions using the Cox proportional hazards model will be performed to determine the independent association of each of the implant variables with LVEF and clinical outcome.

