- **Clinical:** Primary clinical endpoint is a composite of heart failure hospitalization, VT/VF, and any-cause mortality at 12 months.
- **Electrocardiographic:** Change in QRS duration between pre-implant and at hospital discharge, 3 months, 6 months, and 12 months will be performed by readers blinded to treatment allocation. Arrhythmia occurrence (i.e., AF, nonsustained VT, VT or VF requiring device therapy) will be documented throughout the study period
- **Echocardiographic:** Change in left ventricular ejection fraction, chamber dimension, and tissue-strain pre-implant, at 6 months, and at 12 months to be performed by readers blinded to treatment allocation

Primary safety endpoint: Procedure-related complications will be assessed prospectively both acutely and throughout the study period, including:

- **Procedure related:** pneumothorax, perforation, pericardial effusion, or hemorrhage
- **System related:** implant site hematoma, implant site infection
- **Lead related:** lead dislodgement, lead fracture, inability to pace due to high threshold, phrenic capture

Randomization scheme: Patients will be allocated to HBP or standard CS lead at time of implant. Patients with LBBB and non-LBBB will be assigned to separate blocks and randomized separately.

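### The plan names no repeated-measures model or missing-data method for LVEF and QRS, so with visit-wise t tests a 12-month comparison ignores the earlier values of patients lost before month 12

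*Combined protocol and SAP*

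**What the plan says.** Section 2 (Study Design, Primary endpoints) lists "Change in left ventricular ejection fraction, chamber dimension, and tissue-strain pre-implant, at 6 months, and at 12 months" and "Change in QRS duration between pre-implant and at hospital discharge, 3 months, 6 months, and 12 months". Section 5 and the schedule in Appendix B agree: two post-implant echoes, and four post-implant ECGs.

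For the analysis, Section 6 (Statistical methods) says that "continuous parameters will be compared by the two-tailed unpaired Student's t test and the F test for analysis of variance (ANOVA), as needed". The ANOVA is not described as repeated-measures. The regression models named there are logistic and Cox, and neither is a longitudinal model for LVEF or QRS. Kaplan-Meier is planned for event-free survival.

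On loss to follow-up, Section 6 (Sample size estimation) says that "With a significance level (α) = 0.05 and a power of 0.8, at least 17 subjects will be required in each group", and then: "A goal of 40 subjects was made to allow for possible dropout during the study period". No dropout rate is given. The documents name no imputation, no repeated-measures model, no missing-data sensitivity analysis, and no rule for patients who die before an echo. They do not name the visit at which LVEF is to be tested.

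**The concern.** An unpaired t test at 12 months can use only patients who have a 12-month value. For a patient with a 6-month echo and no 12-month echo, the 6-month value adds nothing to that comparison. The same holds for earlier ECGs and QRS duration.

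Enrolling more patients restores the count but not the comparability of those who remain. Loss related to LVEF is plausible in this trial. Patients enter with LVEF of 35% or less and may be in ambulatory NYHA Class IV, and death and heart failure hospitalization are part of the clinical composite. If such loss differs between arms, the 12-month difference is distorted. Section 1.B hypothesizes that the two strategies have similar outcomes, so a difference biased toward zero would wrongly favour that hypothesis, and one biased away from zero would wrongly count against it.

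**Working it through.** **Inputs from Section 6.** Target difference 10 LVEF points; d = 1, so SD = 10/1 = 10; two-sided alpha 0.05; power 0.80; 17 required and 20 planned per arm.

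**Assumed, because the documents do not give them.** The correlation r between 6- and 12-month LVEF (0.7, range 0.6 to 0.8) and the pattern of loss. All 20 per arm are taken to have a 6-month echo. The calculation uses LVEF itself; the listed endpoint is its change.

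**1. The plan's own figure.** The two-sample t test (noncentral t, d = 1) has power 0.781 with 16 per arm and 0.807 with 17, so 17 reproduces. With 20 and no loss, power is 0.869. The implied cushion is (20 − 17)/20 = 15% per arm.

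**2. Bias of the completers' 12-month difference.** If loss depends on the 6-month value, an arm's completer mean shifts by r × SD × (mean standardised 6-month value of those retained). The three lowest of 20 standard normal values have expectations −1.867, −1.408 and −1.131, which sum to −4.406.

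- Three lowest lost in one arm, none in the other: the 17 retained average 4.406/17 = 0.259. Shift = 0.7 × 10 × 0.259 = 1.8. The difference is 10 − 1.8 = **8.2** if the loss is in the lower-LVEF arm and 10 + 1.8 = **11.8** if it is in the higher-LVEF arm. For r = 0.6 and 0.8 the shift is 1.6 and 2.1, giving 8.4 and 7.9 for loss in the lower-LVEF arm.
- Two lowest lost in the lower-LVEF arm, one in the other: 3.275/18 − 1.867/19 = 0.182 − 0.098 = 0.084. Shift = 7 × 0.084 = 0.6; difference **9.4**.
- Three lowest lost in both arms: the shifts cancel; difference **10.0**.

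Simulation (20,000 trials per setting, r = 0.7) agrees to within 0.1. A softer pattern was also simulated, in which a lower 6-month value only raises the chance of loss (10% to 25% loss, r 0.5 to 0.8). The completers' difference was about 8.4 to 9.4 when the rate or pattern of loss differed by arm, with the heavier or LVEF-related loss in the lower-LVEF arm. It was about 10 when rate and pattern were the same.

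**3. Using the 6-month values.** The likelihood (regression-based) estimate that keeps every 6-month echo returned about 10 in all the settings of step 2.

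**4. Precision under random 15% loss in both arms, r = 0.7.**

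- Completers: SE = 10 × √(2/17) = 3.43 (3.42 in simulation).
- With all 6-month values: SE = 10 × √(2 × [(1 − 0.49)/17 + 0.49/20]) = 10 × √(2 × 0.0545) = 3.30.
- The reduction is (3.42 − 3.30)/3.42, about 4%. Approximate power moves from 0.807 to 0.837.

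**5. Where the model fails.** If the three lowest 12-month values are lost in the lower-LVEF arm only, completers give 10 − 10 × 0.259 = 7.4. The model gives 8.6 in simulation, still 1.4 short of the true 10.

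**The case against.** The strongest reply is that the plan is silent on missing data and does not prescribe an analysis of completers. That is correct. A reader might infer that patients lost after an early echo or ECG are discarded. The documents do not support this: 6-month LVEF and the earlier QRS times are themselves listed endpoints, so those values count at their own visits, and the patient's follow-up can enter the Kaplan-Meier analysis. What stands is narrower. The named test cannot use earlier values in a later-visit comparison, and nothing else in Section 6 supplies a method that would.

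A reader might also infer that any loss related to LVEF biases the result. It does not: the same pattern of loss in both arms leaves the difference at 10. The 8.2 and 11.8 come from a deliberately unfavourable case, with all the loss in one arm and exactly the lowest values missing. The milder two-versus-one imbalance costs 0.6 points against an SE of about 3.2. The gain in precision alone would hardly justify a change.

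Finally, a mixed model does not cure loss through death, or loss through worsening after the last echo (step 5 of the working). This stands. It is a reason to add a sensitivity analysis and report deaths, not a reason to keep the t test, which was further from the truth in that case (7.4 against 8.6). The small sample is also a fair caution: an unstructured covariance has 2 × 3/2 = 3 parameters for the two echo visits but 4 × 5/2 = 10 for the four ECG visits, with about 20 patients per arm.

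**Conclusion.** The concern holds as a gap in the analysis plan. Section 6 names a test that ignores earlier visits, provides for loss only through enrolment, and leaves both the main LVEF visit and the handling of deaths unstated.

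The possible bias in the 12-month LVEF difference runs from nothing, when loss is alike in both arms, to about 1.8 points in either direction (18% of the 10-point target) in the extreme one-arm case, with 0.6 points for a two-versus-one imbalance. These figures rest on SD 10 from the plan's d = 1, an assumed correlation of 0.7, and loss that depends on the 6-month value. Loss that depends on the unseen 12-month value could do more harm.

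Two further inferences should be resisted. The sample size is not in error: 17 per arm reproduces, and 20 per arm covers up to 15% loss. Nor do the documents show that differential loss will occur or which way it would push the result. The change is worth making because it is inexpensive.

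**What to change.** In Section 6:

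1. Name the visit for the main LVEF comparison.
2. Replace the visit-wise t tests for LVEF and QRS with one likelihood-based repeated-measures model per endpoint, with arm, visit and arm-by-visit terms. Use an unstructured covariance for the two echo visits, prespecify a simpler covariance as fallback for the four ECG visits, and apply a small-sample degrees-of-freedom correction.
3. Report the 12-month arm difference from the model with its 95% CI.
4. List deaths by arm beside the LVEF result.
5. Add one missing-not-at-random sensitivity analysis, because the model does not resolve values missing through death or through worsening after the last echo.

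The cost is a change of wording and slightly more analysis work, with no new data, visits or patients. The downside is reliance on a missing-at-random assumption, which item 5 is there to probe.

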More recently, the feasibility of resynchronizing ventricular activation by permanent pacing of the His bundle region has been described, with clear clinical advantages over traditional RV apical pacing.¹⁹⁻²³ This technique is an FDA approved therapy for pacing. The physiologic benefit of permanent His bundle pacing (HBP) is the ability to stimulate the ventricles through the intrinsic His-purkinje system, which results in synchronous electrical and mechanical activation. Furthermore, similar to CRT, reports of hyper-response—typically described as patient functional recovery to an LVEF $\geq 50\%$, has been reported with HBP after restoration of normal intrinsic conduction.²⁴⁻²⁶ Perhaps even more provocatively, in a recent study in which patients were implanted with four leads (RA, RV, CS LV lead, and HBP lead), both modes of resynchronization (HBP and CS) were studied utilizing a cross-over design, and both were found to be associated with similar benefit (with patients acting as their own controls).²⁷ Indeed, HBP may have theoretical advantages over CRT using a coronary sinus lead, which is associated with limited coronary venous anatomy and complications that include coronary sinus dissection, venous perforation, and the potential for proarrhythmia. While both techniques comprise the standard-of-care for pacing, direct comparison of HBP with traditional

CS lead position for CRT has not yet been investigated, and is the motivation behind the His-SYNC Study.

B. OBJECTIVES

We hypothesize that:

- a. In patients with advanced heart failure and evidence of intraventricular conduction delay who meet criteria for CRT, HBP may be safely achieved *and*
- b. HBP is associated with similar echocardiographic and clinical outcome as conventional CS pacing during CRT

Specific aims:

Aim 1: To determine the overall rate of successful His-bundle lead placement at the time of implant of CRT. Patients randomized to HBP but who cannot be successfully implanted with a HBP lead will cross-over to traditional CS lead position.

Aim 2: To assess the impact of HBP versus CS pacing on acute and mid-term outcomes.

Acute outcomes include incidence of periprocedural complication and change in QRS duration pre-and post-pacing. Mid-term outcomes include echocardiographic response at 6 and 12 months along with a composite clinical outcome of heart failure hospitalization, arrhythmia, and all-cause mortality.

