2. STUDY DESIGN

Study design: Single-blind study. Patients will be randomized, at the time of implant, to HBP versus CS pacing, and remain blinded to their treatment allocation. Both treatment options use standard-of-care, FDA-approved devices. The distinction is only in the allocation toward HBP and CS pacing. Treating physicians will be aware of assignment in order to facilitate routine device follow-up. Echocardiographic and electrocardiographic evaluation will also be performed in a blinded manner.

Cross-over is permitted between treatment group allocation if:

- CS lead cannot be placed due to difficult cannulation of the CS, limited branches at the posterolateral or lateral wall, or phrenic nerve capture. These patients may then cross-over to HBP.
- HBP patients may cross-over if lead cannot be positioned with adequate stability and reasonable pacing output or if QRS width does not narrow by at least 20% or to a QRS width of \leq 130 msec.

Implant procedure will be per routine percutaneous access, as is standard for pacemaker and ICDs. All patients will receive an FDA-approved cardiac resynchronization therapy pacemaker or defibrillator device, as per standard of care outlined for the patient. In order to facilitate optimal lead placement, arterial access for levo-phase CS angiography and/or LV septal mapping to characterize site of bundle-branch block may also be performed, at the discretion of the implanting physician per his/her standard practice.

Follow-up will be performed at 2 weeks post-implant for incision check and device interrogation as is standard of care. In addition, routine device and clinical follow-up will be scheduled at 1, 3, 6, and 12 months.

Electrocardiography (i.e., ECG) will be performed pre-implant, prior to hospital discharge, at 3 months, 6 months, and 12 months. Echocardiography will be performed pre-implant, 6 months, and 12 months to evaluate for change in LVEF, chamber dimension, and wall motion with strain imaging as is standard of care in the treatment of patients with advanced heart failure. NYHA functional class and quality of life (utilizing the Kansas City Cardiomyopathy Questionnaire) will be assessed pre-implant and at 6 months.

Duration of study: 12 months

Primary endpoints: A combination of clinical, electrocardiographic, and echocardiographic endpoints will be prospectively studied. These include:

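### Patients are compared only by final lead, and only HBP patients may cross over for poor QRS narrowing, so the QRS comparison is biased toward HBP by an amount the documents do not allow one to fix

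*Combined protocol and SAP*

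**What the plan says.** **Analysis groups.** Section 6 (Statistical methods) gives one basis: "Patients will be studied based on the final treatment allocation". It adds that "Crossovers and reasons for crossover will also be recorded", but names no analysis that uses that record. Each implant strategy is to be compared for "its impact on percent change QRS duration, LVEF, and as clinical outcome". No as-randomised, per-protocol or sensitivity comparison appears. Aim 1 (Section 1.B) uses the patients randomised to HBP only to estimate an implant success rate.

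**Crossover rules (Section 2).** For HBP: "HBP patients may cross-over if lead cannot be positioned with adequate stability and reasonable pacing output or if QRS width does not narrow". The narrowing targets are a 20% reduction or a paced width no greater than 130 msec. For CS, the grounds are that the "CS lead cannot be placed due to difficult cannulation of the CS, limited branches at the posterolateral or lateral wall, or phrenic nerve capture". The CS list has no QRS criterion.

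**Endpoint.** The primary endpoints in Section 2 include "Change in QRS duration between pre-implant and at hospital discharge, 3 months, 6 months, and 12 months". Aim 2 is nearer still to the implant measurement: "Acute outcomes include incidence of periprocedural complication and change in QRS duration pre-and post-pacing".

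**Optional or required.** Section 2 words the HBP exit as permission (*may*). Aim 1 words it as a consequence: "Patients randomized to HBP but who cannot be successfully implanted with a HBP lead will cross-over to traditional CS lead position". Section 5 likewise says the alternative site *will* be pursued after an unsuccessful first attempt, without defining unsuccessful.

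**The concern.** A group filtered on QRS narrowing is compared, on QRS narrowing, with a group that receives the patients filtered out. The planned scale (percent change) is also the scale of one of the two exit targets. If the two leads narrow the QRS equally, the final-lead comparison will still tend to show HBP ahead.

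The link is tightest for the acute and discharge ECGs and should weaken for the 3- to 12-month ECGs as follow-up QRS departs from implant QRS. With no randomised-arm comparison planned, the reader has no unselected result to set beside the selected one.

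LVEF and clinical outcomes also lose the protection of randomisation. Whether that biases them, and in which direction, depends on how QRS narrowing relates to them; if it does not, selection on QRS causes no bias.

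**Working it through.** **1. The plan's own figure reproduces.** Section 6 uses an LVEF difference of 10 points with d = 1 (so SD = 10/1 = 10 points), two-sided alpha 0.05 and power 0.8. The noncentral-t calculation gives n = 16.7, hence 17 per group (power 0.81). At 20 per group power is 0.87. The step from 17 to 20 is for dropout only (1 − 17/20 = 15%); there is no allowance for crossover.

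**2. Direction.** Suppose there is no true lead effect and the poorest-narrowing fraction c of the HBP arm moves to CS. Let ρ be the within-patient correlation between narrowing on the two leads, and φ(z_c) the normal density at the c-quantile. Then

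bias in SD units = φ(z_c) × [1/(1 − c) + ρ/(1 + c)].

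For c = 0.30 and ρ = 0.5: 0.348 × (1/0.7 + 0.5/1.3) = 0.348 × 1.813 = 0.63 SD toward HBP. The expression is positive for every ρ from −1 to 1. At ρ = 0.5 it is 0.27 SD at c = 0.10, 0.47 at 0.20 and 0.78 at 0.40.

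**3. Size under the protocol's rule.** The documents give no crossover rate, SD of narrowing or correlations, so all of the following are assumptions: baseline QRS 165 (SD 20) ms; mean narrowing 15–25%, SD 15 points, in both arms; ρ = 0.5; crossing only if both targets (20% and 130 msec) are missed; 20 per arm; pooled two-sample t test; 8,000 simulated trials per scenario. The correlation between implant and endpoint QRS narrowing is r.

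| Use of the QRS exit | HBP patients crossing | r = 1: spurious HBP advantage; p<0.05 | r = 0.7: spurious HBP advantage; p<0.05 |
|---|---|---|---|
| Quarter | 7–13% | 1.9–2.2 points; 7–8% | 1.4–1.6 points; 6–7% |
| Half | 15–27% | 3.9–4.9 points; 13–17% | 2.8–3.4 points; 9–11% |
| Always | 30–54% | 8.8–13.7 points; 45–74% | 6.2–9.6 points; 23–39% |

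Repeat runs move the percentages by one or two, so the last row is summarised as about 22–73%. As a cross-check, 0.63 SD × 15 = 9.5 points at c = 0.30, against 8.8 simulated; the 130 msec alternative blurs the cut. The gap scales with r: 8.8 × 0.7 = 6.2.

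**4. Sensitivity, exit always used.**
- Mean narrowing 30%, SD 12 (15% cross): 4.2 points, 19% at r = 1; 3.0 points, 12% at r = 0.7.
- Rule read as crossing if either target is missed (47–71% cross): 12.6–18.4 points, 72–85% at r = 1; 8.8–13.0 points, 37–47% at r = 0.7.
- Adding 25% CS-to-HBP crossover: 7.5–9.9 points, 37–53% at r = 1; 5.3–7.0 points, 20–28% at r = 0.7.

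**5. The same trials by randomised arm, exit always used.** At r = 1 and ρ = 0.5 the gap is about 2.5 points (8%). With mean narrowing 20% and r = 1 it is about 0 points (5%) at ρ = 1 and 5.5 points (23%) at ρ = 0. What remains is a real effect: the HBP strategy gives poor narrowers a second site.

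**6. Power by randomised arm.** If crossover c is unrelated to response, d = 1 becomes 1 − c. At 20 per arm, power is 0.79, 0.69, 0.58, 0.46 and 0.34 for c = 10, 20, 30, 40 and 50%.

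**The case against.** **The large figures need the exit used every time.** Section 2 makes it optional. At half use and r = 0.7 false positives are 9–11%, and at quarter use 6–7%. If HBP truly narrowed 5 points less, then at half use and r = 0.7 the final-lead result shows HBP worse by 1.6–1.8 points, against 2.6–2.9 by randomised arm, so the two analyses differ by about a point. This stands: the direction is clear, the importance is not. But Aim 1 and Section 5 use *will*, so low use cannot be presumed either.

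**The randomised-arm result is not always null.** Correct. At ρ = 0, mean narrowing 20% and r = 1, it shows 5.5 points (23%) against 9.4 points (45%) by final lead. The contrast between analyses narrows, but the randomised-arm gap is a strategy effect and not selection.

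**Comparing each implant strategy might imply intention-to-treat.** The only grouping Section 6 defines is final allocation, so that phrase does not supply a randomised-arm analysis.

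**The final-lead comparison answers the physiological question.** For QRS it cannot do so without bias, because membership of the HBP group depends on QRS. It remains useful as a secondary analysis.

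**The reach is limited.** Hypothesis b concerns echocardiographic and clinical outcome, not QRS. A reader might infer that the QRS bias undermines the test of that hypothesis; the documents do not support this, because nothing in them ties QRS narrowing to those outcomes by a stated amount.

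**Conclusion.** The concern holds for QRS. The sole planned comparison is by post-crossover lead, and one arm alone has an exit based on a listed primary endpoint, so the QRS comparison is biased toward HBP. With implant-to-follow-up correlation 0.7 to 1 and the base-case assumptions above, the spurious advantage runs from about 1–2 points with near-nominal error (quarter use), through about 3–5 points and 9–17% false positives (half use), to about 6–14 points and 22–73% (always used).

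Three stronger readings are tempting and not supported:
- That the crossover rate alone sets the bias. At full use the gap halves, from 8.8–13.7 points at r = 1 to 4.4–6.9 at r = 0.5, with crossover unchanged. The share of exits made for QRS, the spread of narrowing and both correlations also matter.
- That LVEF and clinical results are biased toward HBP. They lose the protection of randomisation, but no direction or size is claimed.
- That the sample size is miscalculated. The stated 17 per group is right for its inputs; it makes no provision for crossover.

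**What to change.** 1. Replace the Section 6 sentence on analysis groups with: *Comparative endpoints will be analysed primarily by randomised allocation (intention-to-treat), as HBP with CS bail-out versus CS with HBP bail-out. Comparison by final lead will be reported as a labelled secondary analysis, noting that the final HBP group is selected on QRS response. A non-significant intention-to-treat difference will not by itself be read as similarity.*
2. State beside the sample size that the 0.8 power assumes no crossover. Add the power figures for 10–50% crossover as a rough illustration, saying that they treat crossover as unrelated to response, which a QRS-based exit may not satisfy.
3. Reconcile the optional crossover wording in Section 2 with the firm wording in Aim 1 and Section 5. Which rule applies is for the investigators.

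**Cost.** Wording and one line on power. The randomised allocation exists, and crossovers and their reasons are already to be recorded; enrolment and visits do not change. The downside is lower stated power under crossover and dilution of differences toward similarity, which is why the final-lead result stays alongside and non-significance is not to be read as equivalence.

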- Administration of Kansas City Cardiomyopathy Questionnaire
- NYHA functional class to be determined by treating physician

Contact between study visits

- Patients will be enrolled in remote device monitoring (as all CRT patients are) and device alerts will be monitored per routine
- Any hospitalizations will be flagged for review

Future contact

- Patients will be asked to participate in an extended registry to evaluate longer-term clinical outcome after study completion. We will collect data from subjects' medical record for 2 years following their participation in the study. Data collected will include cardiac imaging results, and other clinical events such as hospitalization and death.

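### NYHA class and KCCQ are collected before and after implant but sit in no endpoint, and Section 6's default tests would ignore NYHA's order and KCCQ's baseline score.

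*Combined protocol and SAP*

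**What the plan says.** **Collection.** Section 2 (Study Design) plans NYHA class and "quality of life (utilizing the Kansas City Cardiomyopathy Questionnaire" before implant and at 6 months only. Section 5 (Study Procedures) and the schedule of events in Appendix B add a 12-month assessment of both; the 12-month visit list includes "Administration of Kansas City Cardiomyopathy Questionnaire".

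**Endpoints.** The primary clinical endpoint in Section 2 is an event composite: heart failure admission, VT/VF or death. The composite in Aim 2 (Section 1B) is also built from events. The other endpoints are electrocardiographic, echocardiographic and safety measures. None includes NYHA or KCCQ.

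**Analysis.** Section 6 compares the implant strategies "for its impact on percent change QRS duration, LVEF, and as clinical outcome". Its default rules are "Fisher's exact or the Chi-Square test will be used for categorical variables" and "continuous parameters will be compared by the two-tailed unpaired Student's t test", with ANOVA where needed. Its regression models cover LVEF and clinical outcome. It names no rank, trend or ordinal method. The Study Summary differs: it reserves the Fisher and chi-square tests for dichotomous variables.

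**Raters.** Patients are blinded. Treating physicians know the assignment (Section 2), and they determine NYHA class (Section 5).

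**The concern.** NYHA is an ordered four-level scale, and baseline class varies by design because Classes I to ambulatory IV are eligible (Section 3). An unordered test discards the order, and an unadjusted one discards the baseline. KCCQ is the only patient-reported measure and the one that patient blinding protects most directly, yet nothing fixes which score is used, at which visit, or how baseline enters.

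Two things are at stake. The first is precision: with 20 patients per arm, an inefficient analysis of data already in hand is a real loss. The second is freedom of choice: with no endpoint status, visit or method fixed, what to report about function and quality of life can be decided after the results are seen. Hypothesis (b) in Section 1B concerns similarity of clinical as well as echocardiographic outcome, so both measures bear on it.

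**Working it through.** **Step 1: the plan's own figure.** Section 6 gives "absolute 10% difference in LVEF between the two groups, leading to a Cohen's d statistic of 1", which implies an SD of 10 points, and "With a significance level (α) = 0.05 and a power of 0.8, at least 17 subjects will be required in each group". The normal approximation n = 2(1.960 + 0.842)²/d² with d = 1 gives 15.7, so 16 per arm. The two-sided t test gives 16.71, so 17. The stated figure reproduces. Power is 80.7% at 17 per arm and 86.9% at 20. Enrolling 40 against 34 allows 1 − 34/40 = 15% dropout. This is the only power statement in the documents; there is none for NYHA or KCCQ.

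**Step 2: NYHA, unordered against ordered.** The documents give 20 per arm ("The sample size for this study is a total of 40 subjects (20 HBP and 20 CS lead"). They give no NYHA distribution or effect, so the following are assumptions: CS-arm NYHA I–IV of 20/50/25/5%, and a common odds ratio (OR) shifting the other arm towards better classes.

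The shift works on cumulative odds. The CS cumulative proportions 0.20, 0.70 and 0.95 have odds 0.25, 2.33 and 19. Multiplying by 3 gives 0.75, 7 and 57, that is cumulative proportions 0.429, 0.875 and 0.983. The shifted distribution is about 43/45/11/2%.

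Simulated power at two-sided 0.05, 20 per arm:

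| OR | Unordered chi-square | Rank-sum test |
|---|---|---|
| 2 | 0.12 | 0.19 |
| 3 | 0.28 | 0.43 |
| 4 | 0.41 | 0.60 |

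At 17 per arm and OR 4 the figures are 0.35 and 0.52.

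**Step 3: sensitivity to the assumed distribution.** Three other CS-arm distributions were tried (15/45/35/5%, 25/40/30/5% and 10/50/40/0%), with 2,000 simulated trials per cell. The standard error is at most √(0.25/2000) = 0.011. At 20 per arm:

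| OR | Unordered (chi-square or exact) | Rank-sum |
|---|---|---|
| 2 | 12–14% | 20–22% |
| 3 | 28–32% | 42–46% |
| 4 | 42–47% | 60–62% |
| 6 | 67–72% | 82–83% |

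Type I error was near or below 5% for every test, at most about 6% in simulation. A t test on NYHA scored 1–4 matched the rank test (about 43–46% at OR 3). Collapsing to I/II against III/IV, one way to satisfy the Study Summary's wording, was weakest with Fisher's test: 20–26% at OR 3 and 29–34% at OR 4.

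**Step 4: KCCQ, with and without baseline.** Assume a difference of 0.8 SD and a baseline-to-follow-up correlation of 0.5; neither is in the documents. The unadjusted t test at 20 per arm has power of about 0.69. ANCOVA reduces the residual SD by √(1 − 0.5²) = 0.866, so the effective difference is 0.8/0.866 = 0.92 SD and power is about 0.81. A t test on change scores gains nothing at this correlation, because the variance of change is 2(1 − 0.5) = 1 times that of the follow-up score.

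**The case against.** A reader might infer that the plan prescribes the wrong test for NYHA. It does not: Section 6 never assigns NYHA to any test. The Study Summary's restriction to dichotomous variables would leave a four-level scale without a rule, and if NYHA were scored 1–4, the planned t test would recover the power. The loss therefore belongs to one reading of an unspecified analysis. That objection stands. What remains is that the plan does not choose among readings, and some of them are clearly poorer.

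A reader might also infer that patient blinding protects both measures. It supports KCCQ. NYHA is assigned by physicians who know the allocation, and a more sensitive test does nothing for that bias.

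It is tempting to add that the composite will rest on few events, whereas these scales inform on every patient. The documents give no event rate, they expect dropout, and patients who die have no later score, so neither statement can be relied on.

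The size is also open to challenge. It rests on assumed distributions and fairly large odds ratios; at OR 2 either test is nearly uninformative, and in Step 3 the rank test passes 80% only at OR 6. The simulated rank test had no baseline adjustment, so any further gain from using baseline class is not quantified here. Finally, power to detect a difference is not evidence of similarity; for hypothesis (b), the confidence interval matters more than the test.

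**Conclusion.** The point holds as a low-cost improvement. NYHA and KCCQ are collected without endpoint status, a fixed visit or a named analysis, and Section 6's defaults would use them less efficiently than standard alternatives. If NYHA is treated as categorical at 20 per arm, the unordered test gives up about 15 points of power at OR 3 (0.43 − 0.28) and 19 at OR 4 (0.60 − 0.41), under the assumed 20/50/25/5% distribution. For KCCQ the illustrative gain from baseline adjustment is about 12 points (0.81 − 0.69), under an assumed correlation of 0.5 and effect of 0.8 SD. These figures indicate the order of the loss and do not predict this trial's power. The documents do not support saying that a wrong test is mandated. The LVEF sample size is unaffected.

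**What to change.** 1. In Sections 2 and 6, name NYHA class and the KCCQ overall summary score as secondary outcomes, labelled as such, at one pre-stated visit.
2. Analyse NYHA by a proportional-odds model with baseline class, or a rank-sum test stratified by baseline class. Analyse KCCQ by ANCOVA with baseline score as covariate. Report each between-arm estimate with a 95% interval.
3. Reconcile Section 2 (6 months only) with Section 5 and Appendix B (6 and 12 months) on both measures.
4. Reconcile the Study Summary (dichotomous) with Section 6 (categorical) on the scope of the Fisher and chi-square tests.
5. State that NYHA is rated by treating physicians aware of assignment, so KCCQ, reported by blinded patients, is the less bias-prone of the two.
6. State how deaths and missing scores enter each analysis.

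The cost is wording; no new data are needed if the 12-month assessments in Section 5 go ahead. The downside is two more secondary comparisons.
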